**Aim 2 – Study Visit 2:** We will contact participants on days 23, 25, and 29 to remind participants of their Study Visit 2 appointment. During this study visit, participants will have blood drawn via phlebotomy and placed on a blood spot card in order to assess PrEP adherence. De-identified specimens will be banked for future use in drug abuse screening. We will review digital pill adherence data with participants in Nomi and conduct a pill count to validate adherence data from the digital pill and Reader. We will review discordant counts, periods of Reader activity that suggest no use of the Reader device, and digital pill use with the participant. We will additionally review any potential nonadherent events detected by the digital pill with participants using timeline followback to gauge potential reasons for nonadherence. We will view the adherence interface with study participants and discuss events surrounding potential nonadherence events. We will record user responses to

each of these timeline followback events. We will also dispense an additional 30-day supply of digital pills to participants. We will schedule participants for Study Visit 3 prior to discharge, which will occur a maximum of 30 days (i.e., 23-30 days) after Study Visit 2. Participants will be reminded that we will pass their adherence data along to their PCP; participants will have the option of opting out of this mechanism at each study visit. At the end of Study Visit 2, the participant will be remunerated via a \$25 check.

**Aim 2 – Study Visit 3:** We will contact participants on days 53, 55, and 59 to remind them of their Study Visit 3 appointment. During this visit, we will review adherence data from the digital pill in Nomi, conduct pill counts with participants, address discordant counts and review reader activity with the participants and address any nonadherence events potentially linked to sexual activity or substance use. The participant will receive a final 30 day refill of digital pills and will be remunerated via a \$50 check.

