## **IX. Data Monitoring and Quality Assurance**

We will review and monitor data from DigiPrEP for each study participant. At each study visit, participants will undergo pill counts to correlate adherence data from DigiPrEP, and calculate the accuracy of the digital pill to measure PrEP adherence. Any discrepancies between the digital pill and pill counts will be addressed in real time at each study visit with the participant. For each participant, we will also review signaling from the digital pill to the Reader with our industry collaborator (eTectRx) to ensure there are no errors in data transmission contribution to missed adherence events. If errors occur as a result of data transmission, we will annotate this on the ingestion data.

The study investigators will conduct QA to review data after half of the patients (N=7) of Aim 2/3 are enrolled to ensure that data is accurate and no errors have been made.

The principal investigator ([name]) will be responsible for monitoring adverse events during the study, but Drs. [name] and [name] will assume this responsibility in the event that [name] is unavailable. The role of the responsible person is 1) to identify the concern, 2) develop an appropriate response that involves consultation whenever possible to alleviate or minimize any adverse event, and 3) to ensure that the adverse event is reported in a timely manner to the responsible authority.

Participants will be monitored for occurrence of events defined as any undesirable experience or unanticipated benefit. Events may occur during recruitment, technology deployment, and qualitative interviewing. For example, a participant may become distressed when asked questions about substance abuse and its impact on PrEP adherence. Based upon previous research couched in technology among hidden populations, we anticipate that these effects will be minimal. The principal investigator will assess whether an undesirable experience occurred (adverse event) and will record details of all adverse events (death, life threatening illness, new serious or permanent disability) that occur. Should such an event occur, the principal investigator will report the event within 24 hours to the Fenway Institute IRB.

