DigiPrEP Statistical Analysis Plan

Official title: Feasibility and Acceptability of Digital Pills to Monitor PrEP Adherence in MSM With Substance Use

NCT number: NCT03842436

Document date: September 03, 2021

DigiPrEP Statistical Analysis Plan

Sociodemographics.

Descriptive statistics were calculated for selected variables.

Digital pill system (DPS) performance and engagement metrics.

To analyze the performance of the DPS, the ground truth of PrEP ingestion events were defined as the pill counts obtained each month (i.e., the number of unused pills returned, subtracted from the number of pills previously dispensed). The number of DPS-recorded ingestions – which included the number of both Reader-detected and manually-reported ingestions – was compared with the aggregate pill count at each monthly timepoint; this was defined as the overall performance metric for the DPS. The Reader-detected ingestions count was used to reflect the number of times the DPS was operated correctly. Successful DPS operation was defined as ingestion of a digital pill, proper use of the wearable Reader, and confirmation of the ingestion on both the Reader and the app.

Reader-detected ingestions and manually-reported ingestions that co-occurred within 30 minutes were identified and reconciled; these events likely represented episodes in which a digital pill was ingested, and the ingestion was detected by the Reader, but the participant elected to manually record the ingestion in-app because the Reader was not correctly paired to the smartphone or was delayed in detecting the ingestion. Additionally, several ingestions were manually reported due to a known programming error in the app early in the study. As such, two participants were instructed to manually log all ingestions until an app update was made available; ingestion data for these two individuals were downloaded from their Readers at the end of the study period, and all Reader-detected ingestions were reconciled with manually-reported ingestions.

Participant engagement with the DPS was measured by calculating the total number of DPS-recorded ingestions and comparing the number of monthly DPS-recorded ingestions across each month of the study period.

TFV-DP in DBS.

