We also compared drug concentrations of TFV-DP as measured in DBS at months one and three to DPS-recorded PrEP adherence. First, we identified all DBS samples that, as a result of scheduling challenges, were obtained more than five days after the conclusion of DPS-recorded ingestions, and excluded these DBS samples from analysis, as they resulted in incomplete data to compare with DPS-recorded ingestions. All other DBS samples were paired, based on their collection dates, with the corresponding average of DPS-detected ingestions during the three-week period prior to DBS collection. We dichotomized TFV-DP levels using a cutoff of ≥ 700 fmol/punch to indicate at least four doses of PrEP ingested per week.^{1,2} Using TFV-DP in DBS < 700 vs ≥ 700 fmol/punch as a dichotomous variable, and considering the granular continuous adherence data from the digital pill, we then calculated a point biserial correlation between TFV-DP in DBS and digital pill adherence. Finally, we analyzed the paired TFV-DP concentrations and DPS-recorded adherence data at months one and three, and calculated Pearson's correlation coefficients for each independent timepoint. Analyses were completed using SAS (version 9.4).³

Qualitative analyses.

Qualitative user experience interviews were transcribed and coded using applied thematic analysis.^{4,5} A codebook was generated. All interviews will then double-coded by two study team members; coding was paused and evaluated every five transcripts to ensure consistency and to resolve and document any discrepancies. A kappa statistic was calculated, utilizing a cutoff of > 0.8 to ensure interrater reliability between coders. Coders reviewed aggregate coding to identify and discuss final

themes surrounding user experiences, which were reviewed by the study team as a whole. Qualitative analyses were facilitated by NVivo software.⁶

References

3. SAS Institute Inc. *SAS.*; 2013.

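### The DBS validation reports only correlations, so it shows neither the direction of any recording error nor agreement at the 4-doses-per-week line (minor; a descriptive table would close the gap)

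*SAP*

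**What the plan says.** Protocol VI (Biostatistical Analysis, Aim 2) undertakes to validate ingestion data against dried blood spots (DBS) and names no statistic. The SAP, under TFV-DP in DBS, supplies the method:

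- TFV-DP is cut at 700 fmol/punch "to indicate at least four doses of PrEP ingested per week".
- Each retained sample is paired with the "corresponding average of DPS-detected ingestions during the three-week period prior to DBS collection". Samples taken more than five days after DPS recording ended are dropped; those taken up to five days after are kept.
- DPS adherence stays continuous: "we then calculated a point biserial correlation between TFV-DP in DBS and digital pill adherence". Pearson "correlation coefficients for each independent timepoint" follow, for months one and three.

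The SAP plans no DPS category at four doses a week, cross-table, signed difference or confidence interval. Its only kappa is for interview coders.

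A separate SAP analysis compares DPS-recorded ingestions, "which included the number of both Reader-detected and manually-reported ingestions", with monthly pill counts; "this was defined as the overall performance metric for the DPS". At visits, Protocol V says: "We will review discordant counts, periods of Reader activity that suggest no use of the Reader device". Protocol IX adds: "Any discrepancies between the digital pill and pill counts will be addressed in real time at each study visit with the participant".

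**The concern.** A validation should say whether the device reads low, high or about right against the reference. A correlation says only whether the two measures rise and fall together. The SAP also draws a line on the DBS side at four doses a week, which Protocol I ties to greater than 90% protection, and then does not ask whether the DPS puts the same sample on the same side of it.

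This matters because TFV-DP is the one planned reference that does not derive from returned pills or self-report. Pill counts depend on what a participant brings back, and DPS-recorded counts include manual entries. An error common to both, such as pills removed and logged but not swallowed, could show only against DBS.

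The measure being validated is also not fully clear. The DBS section pairs samples with DPS-detected ingestions but opens and closes with DPS-recorded adherence, which the SAP defines as Reader-detected plus manual.

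**Working it through.** The documents give no power, margin or expected correlation for this comparison, so there is no planned figure to reproduce.

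**Step 1: algebra, no assumptions.** For b > 0, corr(a + bX, Y) = corr(X, Y). If the DPS records the same fraction b of everyone's doses, or is off by the same constant a, both the Pearson and the point-biserial coefficients are exactly those of a perfect device.

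**Step 2: size, under an assumed model.** Doses in 21 days are t ~ Binomial(21, p), with p ~ Beta(8, 1.5), Beta(6, 2) or Beta(4, 2.5) (mean adherence 84/75/62%). TFV-DP = 175 x doses per week x exp(N(0, 0.2)), where 175 = 700/4. The DPS records f x t and is high at 4 or more a week (12 of 21 days, since 4 x 3 = 12). Entries are for the three adherence settings in order.

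| Recorded (f) | Pearson | Point-biserial | Agreement at 4/week, % |
|---|---|---|---|
| 100% | 0.62/0.74/0.84 | 0.53/0.65/0.72 | 93.5/88.4/85.0 |
| 90% | same | same | 92.6/86.4/82.4 |
| 80% | same | same | 90.0/82.1/77.6 |
| 70% | same | same | 68.3/56.4/57.9 |

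Exact invariance fails for other error types. With random misses at 70%, Pearson falls to 0.44/0.60/0.74. With participant-specific detection (mean 0.7, SD 0.15) it falls to 0.32/0.48/0.64. The coefficient weakens but still gives no direction.

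**Step 3: what the discordant cells add.** The expected number per 15 samples is 15 x cell probability. For an accurate device, DPS-low/DBS-high is 15 x 0.007/0.021/0.041 = 0.1/0.3/0.6 and the reverse is 15 x 0.057/0.095/0.109 = 0.9/1.4/1.6. At 70% recorded they are 4.7/6.5/6.3 and 0.1/0.1/0.03. With n = 15 and no recording gap, the chance that DPS-low/DBS-high exceeds the reverse by 3 or more is:

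- accurate device: at most 0.6%
- 90% recorded: 1/9/24%
- 80% recorded: 8/32/53%
- 70% recorded: 87/98/98%

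For a capped 20% over-recording, the chance that the reverse cell leads by 3 or more is 10/37/62%, against 5/13/15% for an accurate device.

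**Step 4: the recording gap.** A sample drawn five days after recording ended has 21 - 5 = 16 observed days. Someone dosing 5 days in 7 then averages 16 x 5/7 = 11.4 recorded doses. That is below 12 although the true rate is 5 a week. With an accurate device, and dosing assumed to continue unrecorded in the gap, a fixed 12-of-21 cut gives a false DPS-low/DBS-high lead of 3 or more in 2/9/22% (3-day gap for all) or 20/52/67% (5-day gap for all). A cut of 4/7 doses per observed day keeps this to at most 6.5%.

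**Step 5: precision.** Protocol II gives N = 15, so there are at most 15 pairs per timepoint. Exact 95% intervals for agreement are 68 to 99.8% for 14/15 and 60 to 98% for 13/15. For Pearson, r = 0.74 gives tanh(atanh 0.74 ± 1.96/√12) = 0.37 to 0.91.

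**The case against.** The strongest reply is that the study can already see bias. The pill-count comparison is the overall performance metric, and discordant counts are reviewed with each participant. If all 90 pills were taken and 70% recorded, the metric would show 0.7 x 90 = 63 of 90. This stands, and it confines the gap to the DBS check. A reader might infer that the plan has no means of detecting recording error, or that the correlations are blind to every kind of error. The documents support neither: the pill-count metric is signed, and random or participant-specific misses do lower the coefficients.

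The second reply is that the table adds little. It is post hoc (the SAP is in the past tense), has at most 15 pairs per timepoint, usually misses 90% recording, and is weak for over-recording, the error for which an independent reference matters most. At high adherence it barely separates a 20% excess from an accurate device (10% against 5%). This also stands, and it keeps the table descriptive. It does not make the correlations sufficient: under a shared proportional or constant error they show neither direction nor agreement at any sample size.

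Third, discordance is not purely device error. TFV-DP noise alone tilts an accurate device slightly towards DPS-high/DBS-low, and the dose-concentration line or unrecorded days can shift the cells too. That limits interpretation but is no reason to leave the cells unreported.

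**Conclusion.** The point holds as a minor one. The DBS validation promised in Protocol VI is incomplete: the two planned coefficients measure association and cannot show the direction of recording error or agreement at four doses a week. The invariance to shared proportional or constant error is mathematical. Every other magnitude rests on assumed adherence, a linear dose-concentration relation, assumed noise and, for the gap results, assumed gap lengths with continued dosing.

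It would go too far to conclude that the DPS is unvalidated or that the trial's main performance result is in doubt. The SAP makes pill counts the ground truth, DBS is a secondary check, and Protocol VI describes a pilot, proof-of-concept study.

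**What to change.** For each timepoint, add a 2x2 table of DPS at or above versus below 4 doses/week against TFV-DP at or above versus below 700 fmol/punch.

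- Compute the DPS rate as ingestions per day of DPS observation within the three-week window, times 7, not as a fixed 12 of 21. Define an observed day by the DPS being in use, not by an ingestion having been recorded; otherwise true missed doses drop out of the denominator.
- Report the gap between the end of recording and each sample, or repeat the table in samples with no gap.
- Give n, both discordant cells, percent agreement and exact 95% intervals, labelled descriptive and post hoc. Add 95% intervals to the Pearson coefficients.
- Use one stated DPS count: Reader plus manual, as the SAP defines DPS-recorded, with Reader-only alongside.
- Read the discordant cells by direction and together with the pill-count comparison.

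The cost is a few lines of text and code on data already held. The write-up should state the limits: wide intervals, sensitivity to large errors only, limited power for over-recording, possibly few samples below 700, and cells that do not isolate device error.
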